#### **10.4.2. Hepatic Safety Analysis**

Hepatic disorders are different and separate from primary efficacy endpoint of hepatic clinical outcomes and are defined as events included in the Hepatic Disorders SMQ, excluding the following sub-SMQs: alcohol related; congenital, familial, neonatal and genetic disorders of the liver; liver infections; and pregnancy-related hepatic disorders.

Summaries will include overall summary of hepatic disorder TEAEs, summary of the incidence of hepatic disorder TEAEs, related TEAEs, TEAEs with CTCAE Grade 3 or higher, TEAEs

leading to treatment discontinuation, TEAEs leading to study discontinuation, SAEs, TEAEs leading to death.

In order to explore the relationship between hepatic disorders and OCA, the following time-to-event analyses will be performed:

- EAIR of custom hepatic queries for PTs “Acute hepatic failure” (hepatic failure) and “Ammonia increased” (hepatic injury)
- Incidence of hepatic TEAEs by PT, and baseline fibrosis status
- Incidence of hepatic SAEs by PT, and baseline fibrosis status

Potential drug induced liver injury (DILI) Triggers: Potential cases of DILI in Study 747-303 are identified via a set of biochemical, adverse event (SMQ based) and study visit questionnaire triggers. These cases then undergo clinical review by the Hepatic Safety Adjudication Committee (HSAC) of all available data for each identified subject to determine liver injury status (including causality and severity).

Summary tables for identified cases will present frequencies of triggers by treatment group as well as highest causality and severity association.

Additional DILI analyses will include the following:

- EAIR of DILI cases adjudicated for ALL cases of hepatic injury by severity and treatment arms
- EAIR of DILI cases adjudicated as  $\geq$  possible causality and severity injury by treatment arms
- Incidence of potential DILI by baseline weight (<85kg, 85-100 kg, and >100 kg)
- Incidence of potential DILI by baseline BMI (<30 kg/m^2,  $\geq$ 30 kg/m^2 to <35 kg/m^2,  $\geq$ 35 kg/m^2)
- Incidence of potential DILI by use of known hepatotoxic medications prior to the event
- Incidence of potential DILI by baseline fibrosis using histology based on original eligibility baseline fibrosis stage.
- Time to onset of first occurrence of adjudicated DILI (Possible, Prob, Highly Likely causality AND  $\geq$  Moderate severity)
- Time to onset of first occurrence of adjudicated DILI (Possible/Prob/Highly Likely causality AND Mild severity)
- Time to onset of first occurrence of adjudicated DILI (Unlikely causality AND  $\geq$  Moderate severity)
- Time to onset of first occurrence of adjudicated DILI (Unlikely causality AND Mild severity)

### 10.4.3. Dyslipidemia

Dyslipidemia adverse events are defined as events included in the dyslipidemia SMQ. Analyses to be performed specifically for dyslipidemia events include:

- Incidence of dyslipidemia TEAEs by PT and presence of dyslipidemia medical history (yes, no)
- Incidence of dyslipidemia SAEs by PT and presence of dyslipidemia medical history (yes, no)
- Incidence of dyslipidemia TEAEs by PT and statin use at baseline (no concomitant use, prior and concomitant use, new concomitant use)
- Incidence of dyslipidemia SAEs by PT and statin use at baseline (no concomitant use, prior and concomitant use, new concomitant use)
- Incidence of LDL increase  $\geq 15\%$
- Incidence of sustained LDL increase  $\geq 15\%$  (defined as present for 2 or more consecutive visits)
- Incidence of dyslipidemia TEAEs preceding any Gallbladder disease and Related Complications TEAE
- KM plot for time to onset of first dyslipidemia TEAE
- Incidence of LDL  $>100$ ,  $>130$ ,  $>190$  post baseline (BL) by treatment group.
- Incidence of LDL increase  $\geq 15\%$

### 10.4.4. Gallbladder Disease and Related Complications

TEAEs of Gallbladder Disease and Related Complications, including cholelithiasis and cholecystitis, are defined as events included in the Gallbladder Related Disorders narrow SMQ and Gallstone Related Disorders narrow SMQ, with additional PTs of Biliary abscess, Biliary sepsis, Biliary tract infection, Gallbladder abscess, Gallbladder empyema, Bile duct necrosis, Bile duct obstruction, Bile duct stenosis, Biliary colic, Cholangitis, Cholangitis acute, Cholangitis chronic, Cholecystocholangitis, and Perforation bile duct.

Specific analyses for gallbladder/gallstone associated events will include:

- Incidence of Gallbladder disease and Related Complications TEAEs by PT and baseline BMI ( $<30$  kg/m^2,  $\geq 30$  to  $<35$  kg/m^2,  $\geq 35$  kg/m^2)
- Incidence of Gallbladder and Related Complications TEAEs by PT and body weight quartiles
- Incidence of Gallbladder disease and Related Complications TEAEs by PT and baseline diabetes status (defined as history of diabetes mellitus at baseline or on antidiabetic medications at baseline with indication of diabetes mellitus or baseline HbA1c  $\geq 6.5\%$ )
- Incidence of Gallbladder disease and Related Complications TEAEs by PT and presence of Gallbladder disease and Related Complications medical history.

- Number and percentage of subjects who underwent a cholecystectomy
- Number and percentage of subjects who underwent a cholecystectomy on or subsequent to adverse event onset day
- KM plot for time to onset of first Gallbladder disease and Related Complications TEAE
- KM plot for time to onset of cholecystectomy.
- KM plot for time to onset of cholecystectomy on or subsequent to gallstone/gallbladder related event onset day

#### 10.4.5. Pancreatitis

Treatment-emergent adverse events of pancreatitis, defined by Acute Pancreatitis narrow SMQ, will be summarized as follows:

- Incidence of pancreatitis TEAEs, by PT and presence of Gallbladder disease and Related Complications medical history (yes, no)
- Incidence of pancreatitis TEAEs, by PT and presence of Pancreatitis (acute or chronic) medical history (yes, no)
- Incidence of pancreatitis TEAEs by PT and presence of Gallbladder disease and Related Complications TEAE (occurring before or simultaneous to Pancreatitis TEAE)
- Incidence of pancreatitis TEAEs by glucagon-like peptide-1 (GLP-1) agonist use (never used, baseline use, initiated during study, baseline use or initiated during study); Note: GLP-1 use initiated during study will only be counted if initiated prior to onset of first pancreatitis TEAE.
- Incidence of pancreatitis TEAEs by shift from baseline to worst post-baseline triglycerides >1000 mg/dL. Note: Only the worst post-baseline triglycerides measurement recorded prior to onset of first pancreatitis TEAE is utilized.
- KM plot for time to onset of first pancreatitis TEAE
- KM plot of pancreatitis cases with on treatment gallbladder Disease or related complications (occurring before or simultaneous to Pancreatitis)

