## 10.4. Adverse Events of Special Interest

The following treatment-emergent AESIs will be summarized:

- Pruritus
- Hepatic
- Cardiovascular
- Dyslipidemia
- Gallbladder disease and related complications
- Pancreatitis
- Renal
- Urolithiases
- Hyperglycaemia/New onset diabetes mellitus

Each subcategory of interest will be defined using Standardized MedDRA Queries (SMQs) and/or custom MedDRA queries, as specified in the subsequent sections.

AESI analyses will include all of the following:

- Incidence of treatment-emergent AESIs by PT
- Incidence of treatment-emergent AESIs by PT and severity
- Incidence of serious treatment-emergent AESIs by PT
- Incidence of treatment-emergent AESIs leading to IP withdrawal by PT
- Incidence of related treatment-emergent AESIs by PT
- Incidence of treatment-emergent AESIs leading to death by PT
- Exposure-adjusted incidence of AESIs by PT
- Exposure-adjusted incidence of serious AESIs by PT
- Exposure-adjusted incidence of AESIs by baseline diabetes status
- Exposure-adjusted incidence of severe (Grade 3+) AESIs by PT
- KM statistics and plot for time to first onset of treatment-emergent AESI
- KM statistics and plot for time to onset of first severe (Grade 3+) or serious treatment-emergent AESI
- KM statistics and plot for duration of first treatment-emergent AESI
- KM statistics and plot for duration of most severe treatment-emergent AESI
- Percentage of subject-days with treatment-emergent AESIs per subject exposure year (SEY), by severity

All summaries noted above will include crude incidence rates for each level of summation. For overall incidence summary of AESI, analyses will be performed separately for AESI collected on-treatment only and during study.

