#### 10.4.6. Renal Injury

Treatment-emergent renal injury is broadly defined as events included in the Acute Renal Failure SMQ, Chronic Kidney Disease SMQ, Proteinuria SMQ, Renovascular disorders SMQ and Tubulointerstitial disease SMQ. Analyses to be performed specifically for renal events include:

- Incidence of renal TEAEs by PT and presence of renal medical history (yes, no)
- Incidence of renal SAEs by PT and presence of renal medical history (yes, no)
- Incidence of renal TEAEs in subjects with >50% increase in serum creatinine from baseline

- Incidence of renal TEAEs by worst change from baseline eGFR ( $\geq 25\%$  reduction from baseline – yes, no); Note: Only the worst post-baseline eGFR measurement recorded prior to onset of first renal TEAE is utilized.
- EAIR specifically for PTs in the broad SMQ “acute renal failure”
- Listing and narratives will be provided for any subjects who had:
  - $\geq 2x$  increase in serum creatinine compared to baseline
  - $\geq 50\%$  decrease in eGFR compared to baseline
  - TEAE of “Nephrolithiasis” (search based on that specific MedDRA PT)

In addition of assessing kidney injury during the trial, the following analyses will be performed, per FDA feedback, to identify a **potential kidney injury**, using the PT terms as noted in [Appendix C](#).

- To assess severity of acute kidney injury (AKI) the following will be provided:
  - Proportion of subjects with TEAE by PT (as noted in Appendix C, [Table C1](#) [List 1]) including risk differences and 95% CIs (using Cochran-Mantel-Haenszel [CMH] method)
  - Proportion of subjects with TEAE by PT (as noted in Appendix C, [Table C2](#) [List 2]) including risk differences and 95% CIs (using CMH method)
- Proportion of subjects who had an action taken due to AKI adverse events including risk differences and 95% CIs (using CMH method)
- Incidence of eGFR decrease  $\geq 25\%$  and  $\geq 50\%$  from baseline by chronic kidney disease (CKD) stage at baseline based on the standard eGFR categories as defined in [Table 7](#) ([Section 10.5.6](#)).
- A listing of subjects who discontinue treatment because of renal dysfunction and their associated last renal lab values while on treatment will be provided by treatment and eGFR decrease.

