#### 10.4.7. Urolithiasis

Treatment-emergent urolithiasis is defined as events included in the high-level group term Urolithiasis (SOC Renal and Urinary Disorders). Analyses to be performed specifically for urolithiasis events include:

- incidence of urolithiasis TEAEs in subjects with  $>50\%$  increase in serum creatinine from baseline prior to urolithiasis.

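### SAP 10.4.5 and 10.4.6: pancreatitis and renal tables by on-study exposure stop the exposure clock at the event for cases but not for non-cases, biasing the exposed-versus-unexposed contrast within each arm toward no risk or protection

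*SAP*

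**What the plan says.** SAP 10.4.5 (Pancreatitis) plans incidence of pancreatitis by three factors that can arise during the study.

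- **GLP-1 agonist use**, in the categories "never used, baseline use, initiated during study, baseline use or initiated during study", with the note "GLP-1 use initiated during study will only be counted if initiated prior to onset of first pancreatitis TEAE".
- **Shift to worst post-baseline triglycerides above 1000 mg/dL**, with the note "Only the worst post-baseline triglycerides measurement recorded prior to onset of first pancreatitis TEAE is utilized".
- **Presence of a gallbladder-related TEAE**, qualified as "occurring before or simultaneous to Pancreatitis TEAE".

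SAP 10.4.6 (Renal Injury) plans incidence of renal TEAEs by whether eGFR fell at least 25% from baseline, with the note "Only the worst post-baseline eGFR measurement recorded prior to onset of first renal TEAE is utilized".

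Two other items carry a similar before-the-event condition: SAP 10.4.7 ("increase in serum creatinine from baseline prior to urolithiasis") and SAP 10.4.2 ("Incidence of potential DILI by use of known hepatotoxic medications prior to the event").

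On the measure, SAP 10.4 says "All summaries noted above will include crude incidence rates for each level of summation". The same section defines an exposure-adjusted incidence rate (EAIR). It ends a case's time at first onset, and a non-case's time at the earliest of last dose plus 30 days, study discontinuation, death or data cut-off. It is specified by treatment group and is not split by any exposure that changes during follow-up.

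**The concern.** Each note shortens the window in which a subject can be called exposed, but only for subjects who have the event. For subjects without it, the SAP gives neither a window nor a denominator. The labels for starting during the study and for the worst post-baseline value read naturally as all of follow-up.

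To be counted as an exposed case, a subject must stay event-free until the exposure occurs. A subject whose event comes first is counted as unexposed, even if exposed later. A non-case has the whole of follow-up in which to become exposed. This is immortal-time bias. It arises inside each arm, so randomisation does not remove it.

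Pancreatitis and renal injury are both adverse events of special interest. A reader will use these rows to judge whether a co-medication, high triglycerides, gallbladder disease or falling kidney function goes with the event. A row that shows no excess, or a deficit, could be taken as reassurance when the layout of the table produced it.

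**Working it through.** The plan gives no figure on this point, so there is nothing to reproduce. The check asks what the table would show if the exposure had no effect.

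**Inputs.** From the documents: the pre-event rules above; minimum follow-up of about 4 years and projected study length of about 10 years (protocol 7.1); visits at Months 1, 3, 6, 9, 12, 15 and 18, then every 6 months (protocol Table 1). Assumed, because the documents give no values: event risk c of 1% to 3%; share p who become exposed during the study of 5% to 30%; exposure and event times independent.

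**Step 1: approximation.** Let the event be rare and both times be uniform over follow-up. Half of the cases who would ever start do so before their event.

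- Risk in starters ≈ c/2.
- Risk in never-users ≈ c(1 − p/2)/(1 − p), because this row keeps the cases whose event came first.
- Ratio = (1 − p)/(2 − p).

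This gives 0.95/1.95 = 0.49 at p = 5%, 0.8/1.8 = 0.44 at p = 20% and 0.7/1.7 = 0.41 at p = 30%.

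**Step 2: worked example, c = 2%, p = 20%.**

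- Starters: cases 0.02 × 0.20 × 0.5 = 0.002; non-cases 0.98 × 0.20 = 0.196; risk 0.002/0.198 = 1.0%.
- Never-users: cases 0.02 × 0.90 = 0.018; non-cases 0.98 × 0.80 = 0.784; risk 0.018/0.802 = 2.2%.
- Ratio 0.45, where the truth is 1.

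**Step 3: constant rates, exact.** Over c of 1% to 3% and p of 5% to 30%, the null ratio is 0.44 to 0.50. With c and p fixed, follow-up of 4, 7 or 10 years gives the same result. Splitting person-time at first exposure gives a rate ratio of 1.00 in every case.

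**Step 4: laboratory version.** With values seen only at protocol visits, a 0.2% to 3% chance of crossing the threshold at each visit, and 48 to 120 months of follow-up, the null ratio is 0.45 to 0.58.

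**Step 5: sensitivity to timing (c = 2%, p = 20%).**

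| Timing | Null ratio |
|---|---|
| Starts mostly late | 0.17 |
| Events mostly early | 0.22 |
| Both uniform | 0.45 |
| Events mostly late | 0.71 |
| Starts mostly early | 0.77 |
| All starts in first 5% of follow-up | 0.97 |

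**Step 6: a real effect.** If exposure multiplies the event rate by h from the start onward, the rare-event ratio becomes h(1 − p)/(2 − p). At p = 20% that is 0.89 for h = 2, 1.33 for h = 3 and 2.22 for h = 5. The exact constant-rate values for p of 5% to 30% are 0.88 to 0.98, 1.31 to 1.47 and 2.15 to 2.43. Split person-time returns 2, 3 and 5.

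**Step 7: baseline GLP-1 users.** Their own risk is not distorted, but the never-used comparator is inflated by the factor (1 − p/2)/(1 − p). At p = 20% the null ratio of baseline users to never-users is 0.8/0.9 = 0.89.

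**Step 8: cell size.** With about 2480 subjects randomised 1:1:1 (SAP 2.2.1), an arm has about 827. At c = 2% that is 16.5 cases, of which 827 × 0.02 × 0.20 × 0.5 = 1.7 fall in the starter row.

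**The case against.** **The open window is inferred.** The SAP does not say how non-cases are classified. This stands. The reading is the natural one, but the sponsor may intend another, and would then need to write it down.

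**The factor of one half is not a property of the plan.** A reader might infer that these tables halve any risk. The documents do not support that: they give no event rates, exposure rates or timing, and step 5 runs from 0.17 to 0.97. Early exposure is plausible for some factors, since protocol 5.5 describes glycaemic rises within the first 3 months of treatment. A factor already present at the first visits would be little affected.

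**Real risk factors would still show.** A reader might infer that any true risk factor is made to look neutral or protective. Step 6 does not support that in general. A doubling can disappear, but a three- or five-fold effect is attenuated and still points to harm.

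**The tables are descriptive.** SAP 10 plans no inferential safety comparisons unless specified, and treatment-group EAIRs, Kaplan-Meier summaries and by-subject listings are also planned. This limits the consequence. It does not make a table sound when its expected ratio under no effect is not 1.

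**The pre-event rule is right in itself.** It keeps out exposure that follows, and may result from, the event. Agreed: what is missing is the counterpart for non-cases.

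**Other items.** A reader might extend the point to 10.4.2 and 10.4.7. The hepatotoxic-medication item names no comparator, and its condition has no meaning for a subject without an event, so it may be a description of cases. The urolithiasis item could be read in the same way.

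**Conclusion.** The point holds for the GLP-1, triglyceride and gallbladder rows in SAP 10.4.5 and the eGFR row in 10.4.6. Followed as written, and with non-cases classified over all of follow-up, the crude exposed-versus-unexposed contrast within each arm is biased toward no risk or apparent protection.

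The direction follows from the rule. The size depends on assumptions: a null ratio of about 0.45 to 0.5 if starts and events are spread evenly over follow-up, and about 0.2 to nearly 1 under other timing. The GLP-1 baseline-use contrast is also affected, more mildly, through the never-used comparator.

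Overall OCA-versus-placebo incidence and the efficacy endpoints are not affected. Items 10.4.2 and 10.4.7 come within the point only if they are meant to compare exposed with unexposed subjects.

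**What to change.** Keep the rule that ignores exposure after the event, and treat these exposures as time-updated.

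1. For each subject, count time before first exposure (drug start, gallbladder TEAE, or first visit at which the threshold crossing is seen) as unexposed and later time as exposed. Assign each event to the status at onset.
2. End everyone's time at the event or at the end of the TEAE window, as the EAIR in SAP 10.4 already does. This also stops a start after that window from counting as exposure in a non-case.
3. Report events, person-time and rates before and after exposure, by arm. A landmark table with the same window for all subjects is an acceptable alternative.
4. For GLP-1, use the same split for the never-used comparator, so that the baseline-use row is compared with a sound reference.
5. State whether the gallbladder row counts a same-day event as exposed, and whether one laboratory crossing makes a subject exposed from then on.
6. State whether the items in 10.4.2 and 10.4.7 are case descriptions. If they are comparisons, treat them in the same way.

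The cost is programming, with no new data and no change to conduct. The EAIR has to be extended, since it is now specified only by treatment group. Small cells will give wide intervals, and laboratory crossings can be dated only to the visit, at 6-month spacing after Month 18.

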#### 10.4.6. Renal Injury

Treatment-emergent renal injury is broadly defined as events included in the Acute Renal Failure SMQ, Chronic Kidney Disease SMQ, Proteinuria SMQ, Renovascular disorders SMQ and Tubulointerstitial disease SMQ. Analyses to be performed specifically for renal events include:

- Incidence of renal TEAEs by PT and presence of renal medical history (yes, no)
- Incidence of renal SAEs by PT and presence of renal medical history (yes, no)
- Incidence of renal TEAEs in subjects with >50% increase in serum creatinine from baseline

- Incidence of renal TEAEs by worst change from baseline eGFR ( $\geq 25\%$  reduction from baseline – yes, no); Note: Only the worst post-baseline eGFR measurement recorded prior to onset of first renal TEAE is utilized.
- EAIR specifically for PTs in the broad SMQ “acute renal failure”
- Listing and narratives will be provided for any subjects who had:
  - $\geq 2x$  increase in serum creatinine compared to baseline
  - $\geq 50\%$  decrease in eGFR compared to baseline
  - TEAE of “Nephrolithiasis” (search based on that specific MedDRA PT)

In addition of assessing kidney injury during the trial, the following analyses will be performed, per FDA feedback, to identify a **potential kidney injury**, using the PT terms as noted in [Appendix C](#).

- To assess severity of acute kidney injury (AKI) the following will be provided:
  - Proportion of subjects with TEAE by PT (as noted in Appendix C, [Table C1](#) [List 1]) including risk differences and 95% CIs (using Cochran-Mantel-Haenszel [CMH] method)
  - Proportion of subjects with TEAE by PT (as noted in Appendix C, [Table C2](#) [List 2]) including risk differences and 95% CIs (using CMH method)
- Proportion of subjects who had an action taken due to AKI adverse events including risk differences and 95% CIs (using CMH method)
- Incidence of eGFR decrease  $\geq 25\%$  and  $\geq 50\%$  from baseline by chronic kidney disease (CKD) stage at baseline based on the standard eGFR categories as defined in [Table 7](#) ([Section 10.5.6](#)).
- A listing of subjects who discontinue treatment because of renal dysfunction and their associated last renal lab values while on treatment will be provided by treatment and eGFR decrease.

#### 10.4.7. Urolithiasis

Treatment-emergent urolithiasis is defined as events included in the high-level group term Urolithiasis (SOC Renal and Urinary Disorders). Analyses to be performed specifically for urolithiasis events include:

- incidence of urolithiasis TEAEs in subjects with  $>50\%$  increase in serum creatinine from baseline prior to urolithiasis.

#### 10.4.8. Hyperglycaemia/New Onset Diabetes Mellitus

Hyperglycemia is defined as adverse events included in the hyperglycaemia/new onset diabetes mellitus narrow SMQ. Analyses to be performed specifically for hyperglycemia/diabetes events include:

- Incidence of Hyperglycaemia/new onset diabetes mellitus TEAEs and SAEs by PT and baseline diabetes status (history of diabetes mellitus at baseline or on anti-diabetic medications at baseline with indication for diabetes mellitus or baseline HbA1c  $\geq 6.5\%$ ).
- Incidence of Hyperglycaemia/new onset diabetes mellitus SAEs by PT and baseline diabetes status (history of diabetes mellitus at baseline or on anti-diabetic medications at baseline with indication for diabetes mellitus or baseline HbA1c  $\geq 6.5\%$ ).
- KM plot for time to onset of first Hyperglycaemia/new onset diabetes mellitus TEAE by baseline diabetes status
- Incidence of initiation of antidiabetic medication in any non-diabetes mellitus subject (no history of diabetes at baseline or not already on medication or HbA1c  $< 6.5\%$  at baseline).
- Incidence of antidiabetic agent intensification (defined as addition of another oral agent/ injectable antidiabetic agent / or insulin) post-baseline in subjects with history of diabetes mellitus or medication for diabetes mellitus at baseline.
- Incidence of treatment emergent HbA1c  $\geq 6.5\%$  by treatment group and time to event post-baseline of HbA1c  $\geq 6.5\%$  by treatment group will be presented.

